Aim 1A quantitative results will be summarized with descriptive statistics. Bivariate analyses will be conducted to assess association of telemedicine features with practice characteristics. In addition to a taxonomy based on the Triangle Model and the Penchansky and Thomas access to care framework,^{2,3} we will also explore a data-driven approach to a taxonomy of implemented telemedicine programs. Here, a 3-step approach will be followed applying two separate data reduction techniques as previously described.⁹ First, multiple correspondence analysis¹⁰ will be applied to study relationships between the (categorical) items in each of the seven conceptual domains of our survey. Where needed, continuous variables will be transformed into categorical variables; this will be distribution-based or based on natural cutoffs. In this step, for each of the seven domains, a select number of factorial axes will be retained for subsequent analyses. This will be based on the percentage of explained variance, interpretability, as well as visual representation of variables and organizations.¹¹ In the second step, the factorial axes that result from the multiple correspondence analysis will be integrated into a principal component analysis. Here, principal components will be retained based on a scree plot (visualizing the percent variance explained by the number of principal components) using the 'elbow criterion'.¹² In the third step, telemedicine programs will be classified using an ascending hierarchical classification method.¹³ This group partitioning technique involves minimizing intra-class variance and maximizing inter-class variance. To obtain the classification, we will inspect the resulting dendrogram (which represents the hierarchy tree) and the inertia quotient (interinertia/total inertia) graph. The latter typically visualizes increases in the inertia quotient (y-axis) with increases in the number of classes (x-axis). Here, we will select the number of classes based on the point after which any increase in the inertia quotient tends to level off. In addition to statistical considerations, decisions regarding the number of classes to retain will also take into account the interpretability of classes⁹. In other words, the number of partitions used in the final classification will take into account both the statistical criterion (inertia quotient) and the theoretical/clinical plausibility of the final groupings. All analyses will be conducted using SAS v.9.4 statistical software (SAS Institute, Cary, NC). These analyses will be conducted and overseen by coinvestigators [name] and [name] [name].

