We will define the degree of telemedicine exposure (dose) in two ways. First, based on the comprehensive landscape survey of primary care leaders in [Aim 1](#), we will develop a composite score indicating the robustness of the telemedicine program at each clinic site under study. Among other features, this score will take into account the total number of components and delivery modes of the telemedicine program, its focus on providing coordinated care to a patient population with chronic care needs, and staff and clinical support from the organization.

Second, we will define telemedicine exposure based on the proportion of all visits at a given clinic that are delivered via telemedicine in each month. Specifically, we will classify clinics into quartiles of telemedicine exposure based on the distribution of all telemedicine provision among clinics in this treatment arm. We will then separately analyze the relationship between our outcomes of interest and the amount (dose) of telemedicine being offered at a clinic. We will cluster all primary and secondary analysis at the clinic level, as this is the level at which the exposure occurred.⁴³

Finally, in addition to the primary intent-to-treat analysis, we are proposing an additional secondary analysis. This secondary “as treated” analysis is designed to evaluate the relationship between patient-level telemedicine exposure and our outcomes of interest. In this secondary analysis, we will characterize patients’ exposure to telemedicine after the first wave of shelter-in-place measures were put into place based on the treatment that they actually received

PRINCIPAL INVESTIGATOR: [name]; [name]

rather than based on the availability of telemedicine at the primary care clinic to which they were attributed. In this analysis, we will adjust for observed clinic and patient-level characteristics as described in the response above that may impact both the availability and choice to use telemedicine, as well as patient outcomes. Additionally, we will provide estimates from a fixed effects model in which each patient serves as their own control.

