Primary findings will be presented alongside descriptive statistics assessing the external and internal validity of the analysis, including balance across relevant covariates before and after matching. We will also use descriptive statistics to characterize the analysis population, identify sources of missingness in the data across outcomes and covariates as well as whether missingness may introduce selection bias into our analysis. In sensitivity analyses, we will multiply impute covariates for which there is meaningful evidence of missingness.

Heterogenous Treatment Effects

We hypothesize that patients in disadvantaged sociodemographic groups will derive less benefit from telemedicine than patients in majority groups because of barriers to use of telemedicine described in the conceptual model. We additionally hypothesize that more robust telemedicine programs (as defined in the Aim 1 taxonomy) will provide more benefit to patients than less robust ones.

We will explore variation in effects for the outcomes listed in Table 1 among pre-specified sociodemographic subgroups (race/ethnicity, rurality, median income for zip code) and clinical subgroups (COVID-19 patients vs. all other patients; low vs. high burden of illness; stable vs. unstable disease, as indicated by clinical measures of disease progression). Finally, we will use the Aim 1 survey for stratified analyses of telemedicine factors, such as historical use of telemedicine and patient technical assistance. Additionally, the Medicare data will allow us to conduct a subgroup analysis for our claims-based outcomes on dually eligible patients. Therefore, we will conduct eight separate subgroup analyses in all. We will use the same analytic approach described in the primary analysis to conduct these subgroup analyses and present the differences in treatment effect estimates with standard errors. We will also conduct univariate subgroup analyses with interaction effects to statistically test for differences in outcomes (as outlined below) among these subgroups.

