Appendix A: Aim 1 Survey Components

Telemedicine domains (I-VII) and sub-domains to be included in our survey; domains are based on the Triangle Model evaluation framework for health information technology (1). References (mostly reviews) are provided for each sub-domain indicating a role in patient outcomes or successful implementation of a telemedicine program. For a subset of sub-domains, relevant Penchansky and Thomas 'access-to-care' framework elements (2,3) are noted that indicate the potential for care access improvement related to these sub-domains. These include: A) affordability, B) accommodation, C) availability, D) accessibility, and E) acceptability.

	Evidence indicating positive effect on outcomes / successful implementation	Relevant Penchansky & Thomas 'access-to-care' framework elements
I. ORGANIZATION (PRIMARY CARE PRACTICE) CHARACTERISTICS		
Location (rural/urban, in states with varying legislation/policies on telemedicine)	54,55	A / D
Patient volume	56,57	C
Ownership (e.g. health system-owned/physician-owned)	55	B
Practice type (e.g. community, academic, FQHC)	55	B
Provider mix (faculty/trainees) [also under II. PROVIDER]	58	B / C

PRINCIPAL INVESTIGATOR: [name]; [name]

Patient mix (insurance, race/ethnicity, age / primary language) [also under IV. PATIENTS]	59	A / E
II. PROVIDER CHARACTERISTICS		
Comfortable with telemedicine (e.g. indirectly measured through previous use of telemedicine in practice)	⁶⁰ [previous use a negative impact]	-
Provider satisfaction with telemedicine (through proxy sources such as complaints or requests for support)	61	-
Provider trainee status (faculty/trainee) [also under I. ORGANIZATION]	58	
III. TECHNOLOGY (TELEMEDICINE) CHARACTERISTICS		
Type		
-Remote monitoring	62-67	B / C / D
-Store-and-forward	62,64	B / C / D
-Interactive telemedicine (video/audio)	62,64,65	B / C / D
-Interactive telemedicine (audio-only)	62,63,64,66	B / C / D
Mode		
-Patient portal	⁶⁸ [potential negative impact] ⁶⁹	B
-App/Software	70	B
-Electronic medical record integration	54,71	-
-Interpreter services (general availability and mode of operation during telemedicine visits)	72	B / C / E
IV. PATIENTS		
Patient mix (insurance, race/ethnicity, age / primary language) [also under I. ORGANIZATION]	59	A / E
Patient access to technology	54,73	B / E
V. ORGANIZATION—TECHNOLOGY RELATIONSHIP		
Leadership engagement	74	-
Needs driven implementation of telemedicine	14,54,59,75	B / C

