Supplementation or substitution of usual care (e.g. in-person visit)	76	-
Identification of 'champions'	54,74,75,77	-

PRINCIPAL INVESTIGATOR: [name]; [name]

Raising awareness among (potential) patients / marketing / outreach (e.g. to get registered onto the electronic medical record platform)	54	B / E
Clarity on candidate criteria ('who is a potential candidate for telemedicine?')	54,78	B
Proactive/pre-emptive vs. reactive scheduling of telemedicine visits	79	B / C
Continuous evaluation of data (processes and outcomes)	75	-
Availability outside of office hours	80	B
De novo implementation or expansion of telemedicine	54	-
Roll-out characteristics (acute/spread out)	73,74	A / B
Long-term plan (e.g. future expansion)		C
Disruption of services (e.g. during encounter)	54,71,74,78	B / C
Patient support services / education (e.g. patient preparation through online resources, on the expected process, troubleshooting mechanisms, instructions in case of disruptions during the encounter, etc.)	54,71,73,75,78	B / C / E
Data security	54,71	
Financial aspects of telemedicine / reimbursement (what is reimbursed and for who and does it matter in terms of telemedicine practice?) / Suitable budget available (e.g. application for FCC COVID-19 telemedicine funding)	54,55,73,77	A / C / E
Collaboration between promoters and users	59	B
VI. PROVIDER—TECHNOLOGY RELATIONSHIP		
Seamless integration into daily routines including services such as scheduling, billing, documentation, check-in/-out process, handling of urgent visits, ordering of laboratory tests/imaging	54,55,59,74	B
VII. ORGANIZATION—PROVIDER RELATIONSHIP		
Provider training	59,73,74,77	-
Support staff	71,73,77,78	-

PRINCIPAL INVESTIGATOR: [name]; [name]

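### Program robustness is defined in two ways, and the robustness contrast is open to confounding by patient mix because no adjustment across robustness levels is stated

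*Combined protocol and SAP*

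**What the plan says.** Two places in Section F define robustness.

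- **Primary Analysis**, in defining telemedicine dose: "we will develop a composite score indicating the robustness of the telemedicine program at each clinic site under study". On content, "this score will take into account the total number of components and delivery modes of the telemedicine program", together with the focus on coordinated chronic care and the staff and clinical support. The list is open-ended.
- **Heterogenous Treatment Effects**: the hypothesis is that "more robust telemedicine programs (as defined in the Aim 1 taxonomy) will provide more benefit to patients than less robust ones". The composite score is not mentioned there.

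Section D (Analytic Methods) describes the taxonomy. One version rests on the Triangle Model and the access-to-care framework. In addition, "we will also explore a data-driven approach to a taxonomy of implemented telemedicine programs". The first step of that approach is to "study relationships between the (categorical) items in each of the seven conceptual domains of our survey". Principal components and hierarchical classification follow, and the number of classes is chosen from the inertia quotient and interpretability. No rule ranks the classes.

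Appendix A lists the survey content. Domain I contains "Patient mix (insurance, race/ethnicity, age / primary language) [also under IV. PATIENTS", and domain IV lists the same item again. Domain V contains "Supplementation or substitution of usual care (e.g. in-person visit".

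Three further statements bear on the contrast:
- Heterogenous Treatment Effects expects sociodemographically disadvantaged patients to gain less from telemedicine, and plans univariate subgroup analyses with interaction effects.
- Primary Analysis matches clinics by propensity score across treatment arms, on rurality, size, clinical risk, Medicaid and dual-eligible shares, age, sex and race/ethnicity.
- Section E (Interventions and Comparators) takes each clinic's arm from the Aim 1 survey.

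**The concern.** A directional hypothesis about more versus less robust programs needs one ordered measure, fixed in advance. The plan has an ordered score in one place. In the place where the hypothesis is stated, it points to a taxonomy that has no stated order. With two candidate definitions, the choice could be made after results are seen.

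The second problem is what the contrast would measure. If more robust programs serve fewer disadvantaged patients, and those patients benefit less (which the plan itself expects), robust programs will look better even when program features have no effect. Nothing in the stated analysis separates the two explanations. Section A promises evidence on the effects of these programs, and Aim 2B asks how effectiveness varies with program features. Patient mix reported as program quality would mislead on both.

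**Working it through.** The documents give no figure for the robustness analysis, so there is none to reproduce. The check compares definitions, counts survey items, simulates the clustering and sets out the confounding route.

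**1. Definitions side by side**

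| | Composite score (Primary Analysis) | Data-driven taxonomy (Section D) |
|---|---|---|
| Scale | Ordered | Unranked classes |
| Named inputs | Components, delivery modes, coordinated-care focus, support | Items from all seven domains, no exclusions stated |
| Patient mix | Not among named inputs | Included, listed in I and IV |
| Supplement/substitute item | Not among named inputs | Included, in V |
| Status | Planned dose measure | Exploratory |

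The framework-based taxonomy does not settle the matter. Appendix A says its domains come from the Triangle Model, and Section D gives no ranking rule for that version either.

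**2. Count of Appendix A sub-domains**

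Domains I to VII: 6 + 3 + 8 + 2 + 17 + 1 + 2 = 39. Patient mix takes 2 of 39 rows and is 1 of the 2 rows in domain IV. The supplement/substitute item is 1 of 39.

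**3. How strongly could those items drive the classes?**

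The three-step procedure of Section D was simulated with 250 practices (the Aim 1A target). The other settings are assumptions: 39 binary items, independent apart from the duplication described below; up to 2 axes per domain; 3 or 5 components; 3 to 5 classes; 200 runs per setting. Mean Cramér's V between class and item was:

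| Item | Handling | Mean V |
|---|---|---|
| Patient mix | Coded identically in I and IV | 0.72 to 0.82 |
| Patient mix | Entered once | 0.18 to 0.25 |
| Patient mix | Left out (chance level) | 0.07 to 0.12 |
| Supplement/substitute | Included | 0.11 to 0.19 |
| Supplement/substitute | Left out (chance level) | 0.08 to 0.12 |

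The patient-mix link can be strong, but mostly through double entry. The link to the arm-like item is weak unless it correlates with other items.

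**4. The confounding route**

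Let p be the share of disadvantaged patients at a robustness level, and e_D and e_A the treatment effects in disadvantaged and other patients. With no program effect, the mean effect at that level is p × e_D + (1 − p) × e_A. Two levels then differ by

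(p₁ − p₀) × (e_D − e_A).

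The documents give neither quantity. Under assumed values, taking absolute sizes:
- shares 60% and 20%, gap 1 point: 0.40 × 1 = 0.4 point
- shares 50% and 30%, gap 0.5 point: 0.20 × 0.5 = 0.1 point
- shares 70% and 10%, gap 1 point: 0.60 × 1 = 0.6 point

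The formula does not depend on how the levels were formed. It applies to the composite score as well if patient mix varies with the score, so changing the definition is not enough without adjustment.

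**5. Does the stated analysis remove this?**

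Difference-in-differences removes stable differences in level between clinics, but not differences in effect. Matching across arms can balance arms, but does not equalize patient mix between robustness levels. A univariate interaction takes one modifier at a time, so a robustness interaction tested this way is not adjusted for patient mix.

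**The case against.** The strongest defense is that the plan already holds a usable measure. The composite score is ordered, and its named contents include neither arm nor payer or race mix. The reference to the taxonomy may be loose wording for the same Aim 1 survey. Aim 2B also relies on single features, such as technical assistance and provider training, which do not depend on any classes. This largely stands, and it is why the remedy is small. It does not remove the mismatch between the two subsections or supply the missing adjustment.

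A reader might infer more than the documents support:

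- **That the test is confounded by construction.** It is not. The clustered taxonomy is exploratory, and the plan does not say which version it means. Bias also requires patient mix to modify the effect or the trend.
- **That the classes are clustered on treatment arm.** The overlap is one survey sub-domain of 39, not the arm variable, and its simulated association is close to chance.
- **That the hypothesis could be neither confirmed nor refuted.** The composite score makes it testable.
- **That Section D is circular in relating features to practice characteristics.** Its bivariate analyses concern individual features, not classes built from those characteristics.
- **That cross-listed items necessarily count twice.** Appendix A lists survey content and marks the cross-listing. Double weight depends on how the items are coded.
- **That domains I, II and IV should be dropped as not describing programs.** Domain II covers previous telemedicine use and domain IV covers patient access to technology. The plan treats historical use as a telemedicine factor.

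**Conclusion.** The concern holds in a limited form. Section F gives two definitions of robustness, and the one attached to the hypothesis has no stated order. Whichever is used, the contrast is open to confounding by patient mix: the plan expects effect modification by sociodemographic group, tests modifiers singly, and balances clinics across arms only.

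The size is unknown. The 0.4-point figure (range 0.1 to 0.6) illustrates the mechanism under assumed shares and effect gaps and is not an estimate for this study. The simulated associations rest on assumed, mostly independent binary items. Overlap with the arm is a minor issue, worth removing because arm status comes from the same survey. Confidence is medium. The primary comparison of the three care models is not affected.

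**What to change.** In Heterogenous Treatment Effects:

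1. Test the robustness hypothesis with the composite score from Primary Analysis, as one ordered interaction term. Fix its components before outcomes are analyzed.
2. Keep patient-mix items and the supplementation/substitution item out of the score.
3. Add interactions of treatment with clinic patient mix, using the covariates already listed for the propensity score. Estimate the robustness contrast within arm or adjusted for arm.
4. Report the taxonomy classes descriptively. If classes are clustered for Aim 2B, enter each cross-listed item once.

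The Aim 1 taxonomy can still be published on all seven domains. The cost is a few extra model terms and slightly wider intervals for the robustness contrast. No new data are needed.

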American Indian	23	12	0	35
Asian	41	29	0	70
Native Hawaiian or Other Pacific Islander	23	13	0	36
Black or African American	190	79	0	269
White	1547	887	0	2434
More than one race	2260	973	0	3233
Unknown or not reported	2688	1482	0	4170
Racial Categories: Total of Hispanics or Latinos	6772	3475	0	10247

*Estimates are counts of ambulatory patients seen at the 4 sites since January 1 2020; due to time constraints, this table includes some patients seen in specialty settings who will not be included in the final analysis.

An additional PCORI deliverable for this project (scheduled for 2021) is to provide a more detailed estimate of patients meeting our eligibility criteria and covered by the two commercial insurers.

Power Calculation

Across participating sites, we estimate about 205,000 patients in primary care with one or more of the five conditions (see **tables** above). For the ED visit outcome, this sample size provides 93% power to detect a 1% difference between the treatment and comparison arms in a two-tailed test with an alpha of 0.05.

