In order to further improve the comparability of clinics across each of the treatment arms, we will use propensity scores to match clinics based on clinic-level characteristics, including rurality; size; mean clinical risk (HCC score, Elixhauser comorbidity index); and proportions of patients with Medicaid coverage, dually eligible for Medicaid and Medicare, 65 and older, male, and black or Hispanic. In an additional sensitivity analysis, we will exclude patients who tested COVID-positive. We will match clinics based on their baseline characteristics in the pre-pandemic period and their initial treatment arm status after the onset of the pandemic. In addition, we will explore the sensitivity of our estimates to re-matching each month, since, as noted in the intervention section above, treatment status will be time-varying. As part of our descriptive analysis, we will evaluate how often clinics switch treatment arms from their initial treatment status, which will inform our sensitivity analyses.

We recognize that it is possible that the matching procedure might result in the loss of clinics and sample size. If it does, we would instead apply alternative methods that accomplish the goal of propensity score matching (addressing confounding to improve causal estimation) without loss of sample size. The first alternative is inverse probability weighting, which uses the propensity score to re-weight the outcomes, creating a pseudo-sample in which exposure to the intervention is unrelated to potential confounders.⁴¹ The second alternative is doubly robust estimation, which incorporates (i) a propensity score model and (ii) an outcome regression model in order to gain efficiency (more power) in comparison to an inverse weighting, and to reduce reliance on the ability of correctly positing the propensity score model.⁴² We can substitute these approaches for the originally proposed propensity score weighting, or we can instead apply them in a sensitivity analysis.

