The goal of these subgroup analyses is to evaluate the effects of each of the three telemedicine arms across patient populations which may have unequal access to telemedicine visits, experience differential treatment effects of telemedicine use, and vary in experiences with regards to using telemedicine. In particular, individuals with lower digital health literacy and higher illness burden may be affected differentially by the adoption of telemedicine-supplemented or telemedicine-only care relative to in-person care only. Previous work has also shown that older adults (aged 65 and older) have lower digital health literacy, and individuals in rural areas are more likely to face greater barriers accessing telemedicine.^{44,45} Previous work has also reported that black patients were less likely to use an inpatient portal relative to white patients, although recent work has shown that during the COVID-19 pandemic, blacks may be more likely than whites to report using telemedicine.^{46,47} We hypothesize that the comparative effectiveness of the treatment arms will differ significantly across the following subgroups: race/ethnicity, rurality, income as proxied by payer and median income for zip code.

G. ETHICS AND DISSEMINATION – AIMS 1 AND 2

Research Ethics Approval

PRINCIPAL INVESTIGATOR: [name]; [name]

BRANY, an independent fully AAHRPP-accredited IRB, will serve as the IRB of record for this study. An exempt approval was received by BRANY on 11/16/2020. Local IRBs will be obtained at the participating sites by the expected deliverable date (2/15/21).

All protocol modifications will be disseminated to relevant parties, including all participating investigators and sites, the IRB, and PCORI.

Confidentiality

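### The effect-modification test for illness burden uses an undefined low/high split; if modification is roughly linear in a normal or right-skewed score, the split discards about a third to a half of the information

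*Combined protocol and SAP*

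**What the plan says.** Section F, Heterogenous Treatment Effects, pre-specifies sociodemographic and clinical subgroups. One of the clinical subgroups is "low vs. high burden of illness". Subgroup estimates are to be presented with standard errors, followed by a formal test: "We will also conduct univariate subgroup analyses with interaction effects to statistically test for differences in outcomes (as outlined below) among these subgroups". The test for illness burden therefore runs on the two-level variable. What follows in that section gives no burden measure, no cut point, no reason for a threshold and no graded analysis.

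The reason for examining burden is that "individuals with lower digital health literacy and higher illness burden may be affected differentially". The hypothesis that closes the section names race/ethnicity, rurality and income. Illness burden is not among them.

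Graded burden scores appear once, in the Primary Analysis section, where the clinic matching variables include "mean clinical risk (HCC score, Elixhauser comorbidity index"). That section also says: "We will cluster all primary and secondary analysis at the clinic level".

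The Power Calculation section covers main effects only. No power is stated for any interaction.

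**The concern.** A two-group interaction treats everyone on the same side of the cut as alike. If the telemedicine effect changes gradually with burden, the variation within each half carries information about that change, and the split does not use it. Interaction tests already have less power than main-effect tests of the same size, so the extra loss makes a false finding of no difference by illness burden more likely. The study wants to say which patients could safely stay with telemedicine, and burden is one of the modifiers it singles out.

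The measure and the cut are also both open. Until they are fixed, the result can depend on choices made after the data have been seen.

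**Working it through.** **Plan's own figure.** There is none to reproduce. The stated power, for example "For the ED visit outcome, this sample size provides 93% power to detect a 1% difference", is for a main effect.

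**Is a graded score available?** A clinic mean of HCC or Elixhauser needs patient-level values. Availability is therefore a sound inference, but the plan does not say that either score defines burden.

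**Information kept by a split.** If modification is linear in the score, the share kept is the squared correlation between the score and the high/low indicator. Let q be the share above the cut.

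- Normal score: kept = φ(z)² / [q(1−q)], where z is the cut on the standard normal scale.
  - Median: 0.3989² / 0.25 = 0.637, so 36% is lost.
  - Top quartile: 0.3178² / 0.1875 = 0.539, so 46% is lost.
- Exponential score: kept = q(ln q)² / (1−q).
  - Median: (ln 0.5)² = 0.480, so 52% is lost.
  - Top 20%, the best of the cuts examined: 0.2 × (ln 0.2)² / 0.8 = 0.648, so 35% is lost.
- Other shapes, by Monte Carlo:

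| Score | Cut | Information lost |
|---|---|---|
| Lognormal, log-SD 0.5 to 1.0 | median | 48% to 73% |
| Lognormal, log-SD 0.5 to 1.0 | top quarter | 39% to 56% |
| Poisson (mean 2 or 4), negative binomial (mean 3) | best cut tried | 33% to 35% |
| Uniform | median | 25% |
| Coarse 1–5 condition count | best cut tried | 27% to 30% |

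**Effect on power.** Power after the split = Φ((1.96 + z_power) × √kept − 1.96). At a normal median split, √0.637 = 0.798.

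- 80% power on the graded score: 2.802 × 0.798 = 2.235, and Φ(0.275) = 61%.
- 90% power on the graded score: 3.242 × 0.798 = 2.586, and Φ(0.626) = 73%.
- Patients needed to restore the power: 1/0.637 = 1.57 times as many.

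**Illustration on the plan's scale.** The 25,000 per arm and the 5% and 20% ED rates come from the non-inferiority paragraph of the Power Calculation section; 10% is an intermediate value. The level is that of "in a two-tailed test with an alpha of 0.05". These are assumptions: two arms, a 1-percentage-point difference in effect between the halves (d = 0.01), modification linear in a normal score, and no clustering.

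- Split: z = d / √(4p(1−p)/12,500).
- Graded: slope per SD = d / (2√(2/π)) = 0.00627, and z = slope / √(2p(1−p)/25,000).

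| ED rate p | z, split | Power, split | z, graded | Power, graded |
|---|---|---|---|---|
| 5% | 2.565 | 73% | 3.215 | 90% |
| 10% | 1.863 | 46% | 2.335 | 65% |
| 20% | 1.398 | 29% | 1.752 | 42% |

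**Clustering and shape.** A simulation used 100 clinics of 60 patients, a clinic-level arm, a within-clinic estimator and cluster-robust errors.

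| Truth | Power, graded (linear term) | Power, median split |
|---|---|---|
| Linear, normal score | 78% | 57% |
| Linear, exponential score | 82% | 48% |
| Step at the median, normal score | 62% | 82% |

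Clustering does not remove the loss. A true step at the cut reverses it.

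**The case against.** **The plan does not tie burden to HCC or Elixhauser.** This stands. A reader might infer that the plan already computes the graded burden score and then throws it away. The text does not support that: the two scores are named only as clinic means for matching, and burden could equally be a count of the five study conditions.

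**The size of the loss is conditional.** This stands. A reader might take a third or more as a general figure. It needs roughly linear modification and a normal or right-skewed score, and the documents give neither. With a step at the cut, a linear term is the worse choice.

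**The rationale need not mean a gradient.** This stands. Saying that people with higher burden may respond differently fits a group contrast as well as a slope. Equally, the plan asserts no step and names no threshold at which one would occur.

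**The power figures depend on chosen inputs.** This stands. The 1-point interaction is not in the documents; their 1-point margin is for a main effect. The plan says of its sample that "we estimate about 205,000 patients in primary care with one or more of the five conditions". Split three ways (about 68,333 per arm), the same formulas give 99% against nearly 100% at a 5% rate, 87% against 97% at 10%, and 64% against 82% at 20%. The footnote to Table 2 says its counts include some specialty patients, so these are upper figures. The calculation also leaves out the third arm, the clustering and the patient-month difference-in-differences structure.

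**The analysis is exploratory.** This stands and limits the weight of the point. Heterogeneity is a secondary analysis, burden is outside the closing hypothesis, and estimates with standard errors will be shown, so a bare verdict of no difference is not the only output. It does not remove the case for a change that costs one model term.

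**Conclusion.** The point holds in a conditional form. The plan tests effect modification by illness burden on a two-level split whose measure and cut are undefined, although graded patient-level scores appear to be available.

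If modification is roughly linear in a normal or right-skewed score, the split discards about a third to a half of the information for that test, and more for a strongly skewed score cut at the median. The loss is about 25–30% for a uniform or coarse count score at a favourable cut, and none for a true step at the cut. The absolute power figures are illustrations and should not be read as the power of this study.

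This is a worthwhile, cheap improvement to an exploratory analysis. It does not affect the primary comparison. The missing definition of the measure and cut needs correcting whichever form of test is chosen.

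**What to change.** In the Heterogenous Treatment Effects section:

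1. Name the patient-level burden measure, for example HCC or Elixhauser, and fix it in the pre-pandemic period.
2. Make the burden interaction test arm by graded score, with a pre-specified log or spline term and clinic-clustered errors.
3. Report the estimated effect at set percentiles of the score, for example the 10th, 50th and 90th.
4. Keep the low/high estimates, with the cut fixed in advance (for example the pre-pandemic median), as a display and a check on functional form.

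The cost is a few lines of SAP wording and one changed model term, with no new data if the scores used for clinic matching serve as the measure. There are two downsides: a functional form must be chosen, and power is lower than with the split if the true effect is a step at the cut. If the team prefers to keep the split as the test, items 1 and the cut in item 4 are still needed.
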